6.2.5 LIDOCAINE WITH EPINEPHRINE

Persons who have previously experienced an allergic reaction to local anesthetics (e.g. with dental procedures) will be ineligible for study participation.

6.2.6 FINANCIAL RISK

The study will be paying for all lab work, fibroblast production, product administration and biopsies required for participation.

6.2.7 CONFIDENTIALITY

Every effort will be made to keep the participants' study information and records safe by following university and HIPAA policy for handling PHI. Participants

will be assigned a unique identifier number which will be used to identify the patient's information as well as their cell samples during the study. The results of this research project may be presented at meetings or in publications; however, participants' identity will not be disclosed. There are no legal risks associated with breach of confidentiality as we are working with healthy volunteers.

6.2.8 TATTOOS

The tattoo markings will be completely excised during the graft removal process. Also, the tattoo procedure will be optional.

6.3 BENEFITS

6.3.1 INDIVIDUAL PARTICIPANT

There will be no benefit to the individual participant.

6.3.2 SOCIETY

The practical goal for this research—creating ectopic volar skin at the stump site of amputees—will occur as a second step to the proposed experiments. In this protocol we will test in a proof-of-concept study in healthy individuals the ability to convert non-volar to volar skin. This in essence is an early phase 1 trial we propose in this investigation. The results will identify the degree and longevity of response which will directly inform the design of future trials. The immediate next trial we propose at the completion of this study will be optimizing again in healthy participants the ideal dose and frequency of cellular delivery in a more formal Phase 1/2 human trial (here optimized only in animal and in vitro models). Only after completion of this second healthy participant study will we attempt a trial on the vulnerable population of amputees. In that trial (Phase 2/3) we will scale up the number and volume of cells to inject according to the increased area of the stump. We predict that this will be feasible given the large increases of cell numbers at later doublings of fibroblast cultures and the use of ring-blocks for anesthesia in an out-patient setting. Importantly we will focus later trials on measuring for increased usability of prosthetics. We are funded for these future trials under DoD AFIRM2.

7. ADVERSE EVENT COLLECTION AND REPORTING REQUIREMENTS

7.1. DEFINITIONS

7.1.1. ADVERSE EVENT (AE)

An adverse event (AE) will be defined as an unusual and undesirable symptom or sign that occurs in participants during the clinical study. Adverse events include those clinically significant laboratory values and test results, concomitant illness, accident, medical occurrence or worsening of existing medical condition that emerge during study participation.

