Through a seedling grant from DARPA we have verified that volar fibroblasts have the ability to induce KRT9 in cells which do not normally do so. We biopsied human volunteers, cultured either volar or non-volar fibroblasts, and added them to foreskin keratinocytes. We detected that just as in normal human skin (Figure 4), palm or sole fibroblasts could induce ectopic KRT 9 (Figure 5). Given that KRT9 is a suprabasal keratin found only in differentiated volar keratinocytes, this strongly supports their use in inducing ectopic volar skin in amputees.

To verify the accuracy of our assay, we have done extensive microarrays. We discovered a master regulatory gene which controls the volar phenotype—the homeobox gene LMX1b. If we knockdown LMX1b then we can now endow even non-volar cells with the ability to induce KRT9 (Figure 6). We have also verified KRT9 inductivity persists through passage 16 of fibroblasts, with one biopsy yielding more than 100 million fibroblasts in a month.

Besides these in 2-D in vitro assays, there is further proof for the inductive power of fibroblasts. In 3-D cultures human volar fibroblasts can make ectopic thickened epidermis and stratum corneum from foreskin keratinocytes (Fig 7). Similarly, Fig 3 demonstrates that non-volar keratinocytes are turned into volar keratinocytes when transplanted to volar fibroblasts. Also Yamaguchi et al demonstrated that human volar fibroblasts could also convert non-volar to volar keratinocytes in a SCID mouse model[2]. We ourselves have performed similar assays where we add mouse keratinocytes either alone or plus inductive fibroblasts and we can show that fibroblasts direct the development of hair growth. These results provide in vivo evidence on how fibroblasts can change epidermal function and control skin identity.

In the course of these studies we have enrolled 11 participants who have had sole/foot biopsies (NA_00033375). Of 11 biopsies, only a single one had a possible infection which was successfully treated with antibiotics. Otherwise there were no adverse events. Therefore we predict a similar safety profile for the currently proposed study.

Phase One - Proposed therapeutic outline:

1. Biopsy palmo/plantar skin at the sole of the foot and the scalp (or other area with suitable non-volar skin) (note higher KRT9 in native tissue in Fig 4 and KRT9 induction in Fig 5)
2. Expand autologous palmo/plantar fibroblasts

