6. RISKS/BENEFITS

6.1 RISKS

6.1.1 AUTOLOGOUS VOLAR FIBROBLASTS

We expect to remove the injected cells, but cellular injections have been rarely associated with mild redness, bruising, swelling, pain, bumps, irritation and itch at the injection site in less than 10% of participants. Injection site reactions may occur including pain, bruising, swelling, erythema, pigmentation changes, induration.

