6.1.3 PUNCH BIOPSY

Common risks of skin biopsies include potential bleeding, pain or discomfort, and a slight risk of infection at the biopsy site. As with any cut in the skin, a scar will develop, although its appearance will likely fade over time.

We will screen carefully for keloids in our exclusion criteria, but in rare individuals with no prior keloid history, keloids or excessive scarring may develop at the biopsy site.

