7.1.2. SERIOUS ADVERSE EVENT (SAE)

A Serious AE (SAE) is any untoward medical occurrence that at any dose produces any of the following outcomes:

- Results in death;
- Is life threatening (defined as an event in which the participant was at risk of death at the time of the event; it does not refer to an event which hypothetically might have caused death if it were more severe);
- Requires inpatient hospitalization or causes prolongation of existing hospitalization (see NOTE below for exceptions);
- Results in persistent or significant disability/incapacity;
- Is a congenital anomaly/birth defect (note: reports of congenital anomalies/birth defects must also be reported on the Pregnancy Supplemental Form);
- Is an important medical event (defined as a medical event(s) that may not be immediately life threatening or result in death or hospitalization but, based upon appropriate medical and scientific judgment, may jeopardize the participant or may require intervention [e.g., medical, surgical] to prevent one of the other serious outcomes listed in the definition above.). Examples of such events include, but are not limited to, intensive treatment in an emergency room or at home for allergic bronchospasm; blood dyscrasias or convulsions that do not result in hospitalization.)

NOTE:

The following hospitalizations are not considered SAEs:

- Admissions as per protocol for a planned medical/surgical procedure;
- Routine health assessment requiring admission for baseline/trending of health status (e.g., routine colonoscopy);
- Medical/surgical admission for purpose other than remedying ill health state and was planned prior to entry into the study. Appropriate documentation is required in these cases;
- Admission encountered for another life circumstance that carries no bearing on health status and requires no medical/surgical intervention (e.g., lack of housing, economic inadequacy, care-giver respite, family circumstances, administrative).

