9.2.1. PRIMARY OUTCOME VARIABLE

The primary outcome variable for this study will be how well the autologous fibroblasts are tolerated by the participants.

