APPENDIX VI- INJECTION SITE PATIENT DIARY

NA_00068684 INJECTION SITE PATIENT DIARY

DATE: _____

PATIENT NAME: _____

DATE	SITE LOCATION	SITE COLOR	SITE SIZE (e.g. Dime, nickel, etc.)	SITE DISCOMFORT (Use table for code)	PHYSICAL SYMPTOMS (i.e. Fever, headache, skin rash, etc)	COMMENTS
	1					
	2					
	3					
	1					
	2					
	3					
	1					
	2					
	3					
	1					
	2					
	3					
	1					
	2					
	3					

REACTION COLOR CODES		DISCOMFORT CODES		SITE DIAGRAM	
A	NO REACTOIN	1	NO DISCOMFORT		
B	LIGHT PINK	2	SWELLING		
C	DARK PINK	3	ITCHING		
D	RED	4	TENDERNESS		
E	PURPLE	5	WARMTH		
F	OTHER	6	OTHER		

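### The AE definition requires a symptom to be unusual, so local reactions judged usual could be left out of the tolerability outcome even though the site diary collects them

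*Combined protocol and SAP*

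**What the plan says.** The primary outcome is given in one sentence in section 9.2.1: "The primary outcome variable for this study will be how well the autologous fibroblasts are tolerated by the participants". Section 9 adds no scale, event list, threshold or safety table. The stopping rule in 9.3 concerns related serious events only.

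Section 7.1.1 defines the unit of safety data: "An adverse event (AE) will be defined as an unusual and undesirable symptom or sign that occurs in participants during the clinical study". A second sentence follows: "Adverse events include those clinically significant laboratory values and test results, concomitant illness, accident, medical occurrence or worsening of existing medical condition", limited to what emerges during participation. Section 7.1.2 begins differently: "A Serious AE (SAE) is any untoward medical occurrence that at any dose produces any of the following outcomes".

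Section 7.2 has the investigator grade severity as Mild, Moderate or Severe. Mild covers events that the participant may notice but that leave daily life unaffected. Section 7.4.1 sends identified AEs to the case report form.

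On the reactions themselves, 6.1.1 first says that reactions to cell injection have been rare, in under 10% of participants. It then adds: "Injection site reactions may occur including pain, bruising, swelling, erythema, pigmentation changes, induration". Participants keep a site diary until excision (5.2.4, Appendix VI), and it is reviewed with the AE assessment at each monitoring visit (5.2.5 and the two visit schedules).

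**The concern.** For a small local injection, tolerability consists largely of local reactions. A definition that asks whether a symptom is unusual works in the wrong direction for this outcome: the more often a reaction occurs, the weaker its claim to be counted. Because only identified AEs reach the case report form, the definition filters events before any are recorded. Because 9.2.1 offers no other measure, what passes the filter is the only graded and attributed evidence on the primary outcome.

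The decision is left to judgement, and under section 4.1.1 the clinicians know which site received volar cells, non-volar cells or vehicle. At stake is whether a low AE count means that the injections were well tolerated or that familiar reactions were not called events.

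**Working it through.** The plan states no figure that depends on the AE definition, so there is nothing to reproduce. The check is a reading of the passages against one another, followed by an attempt to size the loss.

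**1. The test in 7.1.1.** For signs and symptoms, the first sentence joins two conditions with *and*. A reaction that is undesirable but usual fails.

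**2. Does the second sentence restore it?** It lists medical occurrences among AEs. Read as a widening, it would admit any local reaction. Read as examples of what the first sentence covers, it would not. It does not name local reactions or say that known reactions count. The text allows both readings.

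**3. Set against 7.1.2.** The SAE definition starts from any untoward occurrence, with no requirement that it be unusual. SAEs should be a subset of AEs. Under the first sentence of 7.1.1, a serious but usual symptom would be an SAE without being an AE.

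**4. Set against 7.2.** A Mild grade for barely intrusive events suggests that minor reactions were meant to be counted. The word *unusual* pulls the other way.

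**5. From definition to outcome.** 7.1.1 (what is an AE) → 7.4.1 (identified AEs go on the form) → 9.2.1 (tolerability, no measure named). The diary runs alongside this path. Appendix VI records colour, size, type of discomfort, physical symptoms and comments separately for sites 1, 2 and 3. No section says that a diary entry becomes an AE or enters the primary outcome. The gap is in counting, not in collection.

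**6. Size.** The number of participants with an uncounted reaction would be

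M = N × r × u,

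where N is the number injected, r the proportion with a local reaction, and u the share of those whose reactions are all judged usual.

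- N: section 4.1 plans 20 participants for Phase One and says that up to 100 may be consented overall. Those injected may be fewer, because 4.4.1 discharges participants whose cells are not available.
- r: the figure of under 10% in 6.1.1 belongs to its first list of reactions. The second list ("Injection site reactions may occur including pain, bruising, swelling, erythema, pigmentation changes, induration") carries no rate.
- u: not stated. It lies anywhere from 0 to 1.

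With u unknown, M can be zero. The documents do not fix any other value.

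**The case against.** The strongest reply is that 6.1.1 calls reactions to cell injection rare. A rare event is unusual in ordinary language, so on the protocol's own description these reactions would meet the definition. The Mild grade, the reference to medical occurrences, and the mention in 7.4.2 of serious events that are expected (though only serious ones) also point towards counting. This stands as far as it goes: it makes the loss possible rather than certain. It does not remove the word *unusual* or settle which reading of 7.1.1 applies. It also gives least protection if reactions prove more frequent than 6.1.1 supposes.

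It is also fair to say that the AE/SAE mismatch loses no serious events, since 7.1.2 and 7.4.2 capture them under their own definition.

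A reader might infer several stronger things that the documents do not support:

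- *That the sites cannot be compared on tolerability.* They can. The diary is kept by site number, the administration sheet in Appendix V uses the same numbering, and 4.1.1 links each number to what was injected.
- *That the diary prevents grading because its codes give type and not intensity.* Section 7.2 assigns grading to the investigator, who reviews the diary at the visit.
- *That the 11 earlier sole/foot biopsies show under-counting.* Section 3 reports one possible infection and then "Otherwise there were no adverse events", while 6.1.3 says "Common risks of skin biopsies include potential bleeding, pain or discomfort, and a slight risk of infection at the biopsy site". Those biopsies were done under another protocol whose AE definition is not given, and the one event reported is itself a listed biopsy risk.
- *That biopsy reactions are part of the primary outcome.* Section 9.2.1 concerns tolerance of the fibroblasts, not of the biopsy.
- *That the 10% ceiling times enrolment gives the number missed.* That would require every reaction to be excluded, would borrow a rate from a different list, and would treat consented participants as injected.

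**Conclusion.** The point holds as a conflict of definitions that reaches the primary outcome. Section 7.1.1 is narrower than 7.1.2 and at odds with the Mild grade in 7.2. Since only identified AEs are entered on the form and 9.2.1 names no other measure, local reactions judged usual could be omitted from the tolerability result while remaining in the diaries.

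The conclusion assumes that tolerability will be reported from AE records. The documents never say so, but they specify nothing else. It also assumes that an investigator could apply *unusual* as written. Nothing shows that reactions have been or will be dropped, and the documents support no estimate of how many would be. This is a wording fault to correct, and it does not affect the sample size, doses or visits.

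**What to change.** 1. In 7.1.1, replace the first sentence with a definition of an AE as any untoward sign, symptom or medical occurrence during the study, whether or not expected and whether or not related. SAEs then become a subset of AEs.
2. In 7.4.1, state that local reactions found at the diary review are recorded as AEs by site number, with the investigator's 7.2 grade. That section ends AE collection 30 days after the last dose, whereas the diary runs until excision, so the text should say that later diary findings are recorded too.
3. In 9.2.1, name the measure: local reactions tabulated by site (volar, non-volar, vehicle) and grade.

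An intensity column in Appendix VI would help the investigator but is optional.

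The by-site data are already collected, so the cost is a few sentences, one table and a longer AE listing. The reported AE rate will look less favourable.

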7.1.2. SERIOUS ADVERSE EVENT (SAE)

A Serious AE (SAE) is any untoward medical occurrence that at any dose produces any of the following outcomes:

- Results in death;
- Is life threatening (defined as an event in which the participant was at risk of death at the time of the event; it does not refer to an event which hypothetically might have caused death if it were more severe);
- Requires inpatient hospitalization or causes prolongation of existing hospitalization (see NOTE below for exceptions);
- Results in persistent or significant disability/incapacity;
- Is a congenital anomaly/birth defect (note: reports of congenital anomalies/birth defects must also be reported on the Pregnancy Supplemental Form);
- Is an important medical event (defined as a medical event(s) that may not be immediately life threatening or result in death or hospitalization but, based upon appropriate medical and scientific judgment, may jeopardize the participant or may require intervention [e.g., medical, surgical] to prevent one of the other serious outcomes listed in the definition above.). Examples of such events include, but are not limited to, intensive treatment in an emergency room or at home for allergic bronchospasm; blood dyscrasias or convulsions that do not result in hospitalization.)

NOTE:

The following hospitalizations are not considered SAEs:

- Admissions as per protocol for a planned medical/surgical procedure;
- Routine health assessment requiring admission for baseline/trending of health status (e.g., routine colonoscopy);
- Medical/surgical admission for purpose other than remedying ill health state and was planned prior to entry into the study. Appropriate documentation is required in these cases;
- Admission encountered for another life circumstance that carries no bearing on health status and requires no medical/surgical intervention (e.g., lack of housing, economic inadequacy, care-giver respite, family circumstances, administrative).

7.1.3. NON-SERIOUS ADVERSE EVENT

A non-serious adverse event is any adverse events not classified as serious (as described in previous section). All non-serious AEs will be reported to the IRB on an annual basis with the continuing review.

7.2. ADVERSE EVENT GRADING

Adverse events will be identified and graded using the schema described below. The investigator will evaluate the severity of any adverse event using the following definitions:

- *Mild* - event may be noticeable to participant; does not influence daily activities; usually does not require intervention.
- *Moderate* - event may be of sufficient severity to make participant uncomfortable; performance of daily activities may be influenced; intervention may be needed.
- *Severe* - event may cause severe discomfort; usually interferes with daily activities; participant may not be able to continue in the study; treatment or other intervention usually needed.

AEs graded as ‘severe’ which are possibly, probably, or definitely attributable to the use of the investigational drug will be recorded and monitored until the event has resolved to meet the definition of ‘mild’. All participants will receive care for all adverse events according to good clinical practice as per the standard of care at Johns Hopkins.

7.3. ATTRIBUTION OF ADVERSE EVENTS

All adverse events will be further evaluated for attribution as per the following:

- Unrelated: Adverse event is clearly not related to the investigational agent.
- Unlikely: Adverse event is doubtfully related to the investigational agent.
- Possibly: Adverse event is possibly related to the investigational agent.
- Probably: Adverse event is probably related to the investigational agent.
- Definitely: Adverse event is definitely related to the investigational agent.

7.4 ADVERSE EVENT CAPTURE AND REPORTING

7.4.1. ROUTINE ADVERSE EVENT CAPTURE AND REPORTING

The collection of all AE information begins at initiation of investigational product and continues during the clinical study until 30 days of receiving the last dose of study medication.

If an ongoing AE changes in its intensity or in its perceived relationship to investigational product, a new AE entry for the event will be completed. Adverse events will be followed to resolution or stabilization, or reported as SAEs if they become serious. Follow-up is also required for AEs that cause interruption or discontinuation of investigational product, or those that are present at the end of study participation. Participants with AEs at study completion will receive post-treatment follow-up as appropriate.

All identified AEs will be recorded and described on the appropriate Case Report Form (CRF). Non-serious adverse events will be logged and reported to the IRB on an annual basis. FDA will receive an annual report within 60 days of the anniversary of IND approval each year as per regulation.

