4.5 STUDY DURATION AND REQUIRED VISITS

Participants will be considered ‘on-study’ once informed consent has been obtained. The duration of the study for each participant will begin at the time of consent and continue until completion of the final study evaluation.

For Phase One participants: At a minimum, there will be 7 study visits, including screening procedures. At a maximum, there will be 12 study visits over a period of 10 months.

For Phase Two participants: At a minimum, there will be 4 study visits, including screening procedures. At a maximum, there will be 14 study visits over a period of 12 months.

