6.2 STEPS TAKEN TO MINIMIZE RISK

6.2.1 AUTOLOGOUS VOLAR FIBROBLASTS

Injected cells will meet all required release criteria for clinical use before injection (see IND application which includes steps of verifying purity, sterility and potency) by the Hopkins Cellular Therapy Core. Additionally, we will remove the injected site via biopsy in order to avoid any theoretical long-term problems from injected cells. Finally, all participants will be closely monitored for adverse events throughout the study.

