7.4.2. SERIOUS ADVERSE EVENT CAPTURE AND REPORTING

ALL serious adverse events, regardless of causality will be reported to the IRB per the JHM IRB reporting requirements. Prompt reporting to the JH SOM IBR of unanticipated problems and SAEs will occur as soon as possible after the PI learns of the event, but in all cases within 10 working days with the exception of death of a JHM participant. In this instance, reporting requirements defined in [Policy 103.6\(b\)\(i\) will be followed.](#)

Serious and expected adverse events will also be reported to FDA as soon as possible and no later than 15 calendar days after the sponsor's initial receipt of the formation. Serious unexpected adverse events will be reported immediately upon learning of the event via phone/fax and within 7 days via MedWatch 3500A.

Also, all SAEs will be immediately reported to our named internal Safety Monitor, [name], MD. [name] is a dermatologist with extensive experience in clinical trials as a PI on more than 10 active IRB protocols. She will provide independent authority to stop the trial, remove any participants from the trial, and otherwise maximally ensure patient safety within the limits of the protocol.

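### The adverse event collection window in 7.4.1 contradicts the AE reviews required from Day 0 to Day 273, and 9.2.1 does not say which period the primary tolerability outcome covers

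*Combined protocol and SAP*

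**What the plan says.** All references are to the combined protocol and SAP.

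- **The window.** Section 7.4.1 opens by saying that collection of AE information of every kind "begins at initiation of investigational product and continues during the clinical study until 30 days of receiving the last dose of study medication". Its last paragraph says "All identified AEs will be recorded and described on the appropriate Case Report Form (CRF", with no time limit.
- **The visits.** AE assessment is listed at Day 0 (5.2.2), at Day 14 (5.2.3), at each monitoring visit (5.2.5 to 5.2.5.5), at the Day 182 graft removal (5.2.5.6) and at the final evaluation (5.2.7). The AE row of the Phase One and Phase Two schedules (Appendices I and II) runs from Day 0 to Day 273. The text of 5.2.6 (Day 196 suture removal) lists no AE item, but both schedules mark one.
- **The definitions.** Section 7.1.1 reads "An adverse event (AE) will be defined as an unusual and undesirable symptom or sign that occurs in participants during the clinical study". Section 4.5 has each participant's study duration "begin at the time of consent and continue until completion of the final study evaluation". Section 6.2.1 states that "all participants will be closely monitored for adverse events throughout the study".
- **Rules with no time limit.** Under 7.2, AEs graded severe that are "possibly, probably, or definitely attributable to the use of the investigational drug will be recorded and monitored until the event has resolved" to mild. Section 7.4.2 says "ALL serious adverse events, regardless of causality will be reported to the IRB per the JHM IRB reporting requirements".
- **The outcome.** Section 9.2.1 reads "The primary outcome variable for this study will be how well the autologous fibroblasts are tolerated by the participants". It gives no observation period.

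**The concern.** The section that sets the AE collection rule opens with a window much shorter than the follow-up the same protocol schedules. The primary objective is safety and tolerability. Two members of staff could each follow the text and record different events: one stops at 30 days after the last dose, and the other records whatever the scheduled reviews find. The primary tolerability summary would then depend on which sentence was used.

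The start of the window matters too. Three biopsies are taken at Day 0 (5.2.2), about a month before any product. In the earlier work described in the Background, one of 11 sole or foot biopsies had a possible infection. Such an event here would come before the 7.4.1 start. Under 4.4.1, participants whose cells fail to expand leave without receiving product, so under the start sentence their AE collection never begins. Biopsy events do not measure how well the fibroblasts are tolerated, but they belong in the trial's safety record.

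**Working it through.** The plan gives no figure of its own here, so the check compares dates. Study days are nominal unless stated.

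**Inputs.** Injection is on Day 30 in Phase One and on Days 30, 37, 42 and 59 in Phase Two (5.2.4). Graft removal is on Day 182 (5.2.5.6), suture removal on Day 196 (5.2.6) and final evaluation on Day 273 (heading of 5.2.7). The schedules allow ±10 days on injection, whereas 5.2.4 gives ±7 for Phase One. Section 5.2.4 also lets Phase Two injections be spread over 30 days.

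**Step 1: the 7.4.1 window.** Close = last injection + 30.
- Phase One: 30 + 30 = Day 60. With injection on Days 20 to 40, the close is Day 50 to Day 70.
- Phase Two: 59 + 30 = Day 89. With a single dose on Day 30, the close is Day 60.
- Latest close: a first dose on Day 40 and a last dose 30 days later on Day 70 give 70 + 30 = Day 100.

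**Step 2: which reviews fall outside.**
- Before the window in both phases: Day 0 and Day 14 (Day 15 in the schedules).
- After the window, Phase One: Days 70, 98, 126, 154, 182, 196 and 273. Day 42 is inside.
- After the window, Phase Two with last dose on Day 59: Days 98, 126, 154, 182, 196 and 273. Day 70 is inside.
- Earliest dates for the last three scheduled visits: 182 − 7 = 175, 196 − 7 = 189 and 273 − 14 = 259. All are later than Day 100, so these visits are outside at any permitted dosing date.

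**Step 3: share of the graft period left uncovered.** Share = (removal day − close) / (removal day − 30), set to 0 where removal comes before the close.

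| Removal day | Phase One, close Day 60 | Phase Two, close Day 89 |
|---|---|---|
| 182 | 122/152 = 80.3% | 93/152 = 61.2% |
| 98 | 38/68 = 55.9% | 9/68 = 13.2% |
| 70 | 10/40 = 25.0% | 0% |
| 42 | 0% | not a monitoring visit in the Phase Two schedule |

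A Phase Two participant given one dose on Day 30 and removal on Day 182 has the Phase One share, 80.3%. With the latest dosing (first Day 40, last Day 70, close Day 100), the share at Day 182 is (182 − 100)/(182 − 40) = 82/142 = 57.7%.

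The schedules' excision row starts at Day 98, but 5.2.5 ties early removal to whichever monitoring visit shows significant thickening. The table therefore goes below Day 98.

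**Step 4: which events are exposed.** SAEs (7.4.2) and severe AEs at least possibly attributable to product (7.2) have their own rules, with no time limit. Section 7.4.1 follows events begun inside the window to resolution or stabilization. That leaves new mild or moderate AEs, and severe AEs judged unrelated or unlikely related, that arise outside the window.

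**The case against.** The strongest reply is that one sentence stands against many consistent ones. For an event to be lost, staff would have to carry out a required AE assessment and then leave out what it found, against the closing paragraph of 7.4.1. That part stands: a reader might infer that late AEs will be lost, or that late safety is not monitored, and the documents support neither. The loss occurs only if the stop sentence is applied. The reply does not remove the contradiction, because the stop sentence is in the section that governs collection and nothing ranks it below the others. Its phrase about continuing during the study is cut off by the 30-day limit, and following ongoing events does not reach new ones.

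Three other stronger readings also fail.

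- A reader might say that every monitoring visit is outside the window. Phase One Day 42 and Phase Two Day 70 are inside, and with injection on Day 40 the Phase One Day 70 visit is reached as well.
- A reader might measure from first injection to Day 273, giving 213/243 = 88% and 184/243 = 76%. Of those 243 days, 273 − 182 = 91 follow the scheduled excision, when wound healing is the main thing observed. The graft-period shares bear more directly on fibroblast tolerability. A count of Phase Two reviews is also unsafe, because Appendix II shows Visits 3 to 6 as one merged column.
- A reader might conclude that the tolerability summary has to run to the final evaluation. The documents do not dictate this. They support stating a period, and closing it at graft removal is also defensible.

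**Conclusion.** The contradiction is real, and no section resolves it. It should be fixed, but it is a defect of wording and not evidence that safety data will be lost.

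If the stop sentence is applied, non-serious AEs of the kinds in Step 4 are not collected before first product or later than 30 days after the last dose. With removal on Day 182, that leaves about 80% of the graft period uncovered in Phase One and 61% in Phase Two with a last dose on Day 59. Early removal lowers these shares, to 0% at the extreme. The scheduled excision, suture removal and final evaluation are outside in every case.

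The figures assume the following.
- Removal is on Day 182. Section 5.2.5 also speaks of removal at 10 months, which would raise the shares.
- Day 273 is a study day. The body of 5.2.7 counts it from initial injection, about Day 303, which is also outside.
- The AE row of Appendix I is read by its clear first and last visits. It shows one mark more than there are visit columns, probably from text extraction.

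**What to change.** 1. **Section 7.4.1.** Reconcile it with 5.2 and the schedules so that AE collection runs at least from the Day 0 biopsy through the final evaluation visit. Starting at consent would also match 4.5 and 7.1.1 and would cover the screening blood draw.
2. **Section 5.2.6.** Add AE assessment to the text so that it matches the Day 196 column of both schedules.
3. **Section 9.2.1.** State the period that the primary tolerability summary covers. It should run from first injection and extend past the 30-day cut-off, at least through graft removal. List harvest-biopsy and excision-wound events separately. Whether the summary ends at removal or at the final evaluation is for the sponsor to choose and state.

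The cost is wording in three sections and possibly a higher reported AE count. No visits are added, because the schedules already mark AE review at each one from Day 0 onward.
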